#### 2.4.5 Analyses of safety data

Safety data will be summarized descriptively for each study [REDACTED] separately. The summary of safety results will be presented by dose regimen cohort. Further subdivision by weight group will be performed only for selected parameters given the small sample size.

Safety summaries during the entire TEAE period will be provided. In addition, summaries on the important safety events will also be provided by time periods including 0-12 weeks, 0-24 weeks, and 0-52 weeks; details are provided in [Section 2.4.5.6](#). For the analyses on 0-52 weeks and entire TEAE period, summaries on the non-selected doses will only include the data collected prior to the first dose adjustment to the selected dose; a combined 'any dose' group will be added to summarize all the safety data for all treated patients. In addition, data after the dose adjustment will be summarized separately ([Section 2.4.11](#)).

##### *General common rules*

All safety analyses will be performed on the safety population as defined in [Section 2.3.2](#), unless otherwise specified, using the following common rules:

- The baseline value is defined as the last available value prior to the first dose of the study medication.
- The potentially clinically significant abnormality (PCSA) values are defined as abnormal values considered medically important by the Sponsor according to predefined criteria/thresholds based on literature review and defined by the Sponsor for clinical laboratory tests and vital signs ([Appendix A](#)).

- PCSA criteria will determine which patients had at least 1 PCSA during the TEAE period, taking into account all evaluations performed during the TEAE period, including nonscheduled or repeated evaluations. The number of all such patients will be the numerator for the on-treatment PCSA percentage.
- The treatment-emergent PCSA denominator by group for a given parameter will be based on the number of patients assessed for that given parameter in the TEAE period by dose regimen cohort on the safety population.
- For quantitative safety parameters based on laboratory measurements, descriptive statistics will be used to summarize result and change from baseline values by visit and dose regimen cohort. Summaries will include the endpoint value. The endpoint value is commonly defined as the value collected at the same day/time of the last dose of IMP. If this value is missing, this endpoint value will be the closest one prior to the last dose intake.
- Analyses of the safety variables will be essentially descriptive and no systematic between-group testing is planned.

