Day	D 113 (±1 or 3)	D 141 (±1 or 3)	D 169 (±1 or 3)	D 225 (±1 or 3)	D 281 (±1 or 3)	D 337 (±1 or 3)	D 421 (±1 or 3)	D 505 (±1 or 3)	D 589 (±1 or 3)	D 673 (±1 or 3)	D757 (±1 or 3)	D 841 (±1 or 3)	D 925 (±1 or 3)	D 1009 (±1 or 3)	Wk 156/EOT	EOS: WK162/EOT+6 Wks
Week	Wk 16	Wk 20	Wk 24	Wk 32	Wk 40	Wk 48	Wk 60	Wk 72	Wk 84	Wk 96	Wk 108	Wk 120	Wk 132	Wk 144		
ANA/anti-dsDNA antibody ^l			X			X		X		X					X ^l	
Local urine pregnancy test for females who are menstruating ^m	X	X	X	X	X	X	X	X	X	X	X	X	X	X	X	
Pharmacokinetics and ADA																
Serum sarilumab ⁿ			X			X		X		X		X			X	X
Antibodies to sarilumab ⁿ			X			X		X		X		X			X	X

Abbreviations: ADA = anti-drug antibody, AE = adverse event, ALP = alkaline phosphatase, ALT = alanine aminotransferase, ANA = antinuclear antibodies, ANC = absolute neutrophil counts, AST = aspartate aminotransferase, BP = blood pressure, DNA = deoxyribonucleic acid, D = day, EOT = End-of-Treatment, EOS = End-of-Study, ESR = erythrocyte sedimentation rate, hs-CRP = high sensitivity C-reactive protein, IMP = investigational medicinal product, IVRS = Interactive Voice Response System, JADAS = Juvenile Arthritis Disease Activity Score, JIA ACR = Juvenile Idiopathic Arthritis American College of Rheumatology, PK = pharmacokinetics, PPD = Purified Protein Derivative, SAE = serious adverse event, TB = Tuberculosis, V = visit, Wk/Wks = week, yrs = years.

- Visit 27 (Week 156) is the study planned End-of-Treatment (EOT) visit. If patients discontinue the study treatment prematurely, EOT will occur 1 week after the last IMP injection for Dose Regimen 3 Cohort and 2 weeks after the last IMP injection for Dose Regimen 1 and 2 Cohorts.
- Visit 28 (Week 162) is the study planned End-of-Study (EOS) visit. If patients discontinue study treatment prematurely, these patients will be asked to return for the End-of-Study (EOS) assessment 6 weeks after the EOT visit (EOT+6 weeks). This EOS visit will be applicable to all the patients in both core treatment phase and extension phase.
- Home diary for IMP administration to be completed for IMP administered at home.
- Complete physical examinations will be performed at Visit 15 (week 24), Visit 18 (Week 48), Visit 20 (Week 72), Visit 22 (Week 96), Visit 24 (Week 120), Week 26 (Week 144), and Visit 27 (Week 156) including skin, nasal cavities, eyes, ears, respiratory, cardiovascular, gastrointestinal, neurological, lymphatic, and musculoskeletal systems.

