- Investigational medicinal product (IMP) to be administered once every two weeks for patients in Dose Regimen 1 and 2 Cohorts and once every week for patients in Dose Regimen 3 Cohort. Patients should be monitored for at least 30 minutes after IMP administration for any signs or symptoms of a hypersensitivity reaction. For patients who complete the extension phase, if the selected dose regimen is dosed once every other week (q2w), then the last IMP injection will occur at Week 154, if the selected dose regimen is dosed once a week (qw), then the last IMP injection will occur at Week 155. Patients will have EOT assessment at the Visit 27 (Week 156). For patients who discontinue the study treatment prematurely during the extension phase, it will be preferable to have EOT assessment 2 weeks after the last IMP injection for Dose Regimen 1 and 2 Cohort patients and 1 week after the last IMP injection for Dose Regimen 3 Cohort patients. In case the patient is unable to meet the planned schedule, the EOT visit

will be used for assessment at the next protocol-defined visit after the last IMP injection. Patients will be asked to return to the site for the EOS assessment 6 weeks after the EOT visit. There will be no IMP injection at the Visit 27 (Week 156).

- f. Height will be measured using stadiometer at sites during the study.
- g. Juvenile Idiopathic Arthritis American College of Rheumatology (JIA ACR) core set includes: global assessment of the severity of disease by the physician, global assessment of overall well-being by the patient or parent, number of joints with active arthritis (defined as swelling within the joint not due to deformity OR limitation of motion and with either pain, tenderness, or both), number of joints with limitation of motion, Childhood Health Assessment Questionnaire (CHAQ), and hs-CRP (2.3.4). If a patient discontinues prematurely before Week 96, hs-CRP must be performed by the central laboratory at EOT.
- h. Juvenile Arthritis Disease Activity Score scoring is explained in [Section 9.4.2](#).
- i. Hematology (blood should be drawn PRIOR TO drug administration): Hemoglobin, hematocrit, red blood cell (RBC) count and morphology (if RBC count is abnormal), white blood cell (WBC) differential (neutrophils, lymphocytes, monocytes, eosinophils, basophils), platelet count, absolute neutrophil count (ANC). If a patient discontinues prematurely before Week 96, the test must be performed by the central laboratory at EOT.

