- g Investigational medicinal product (IMP) to be administered once every other week (q2w). Patients should be monitored for at least 30 minutes after IMP administration for any signs or symptoms of a hypersensitivity reaction. The last IMP injection will occur at Week 94; then patients will have EOT assessment at the Visit 27 (Week 96 for third portion). There will be no IMP injection at the Visit 27.

- h* Height will be measured using stadiometer at sites during the study.
- i* Juvenile Idiopathic Arthritis American College of Rheumatology (JIA ACR) core set includes: global assessment of the severity of disease by the physician, global assessment of overall well-being by the patient or parent, number of joints with active arthritis (defined as swelling within the joint not due to deformity OR limitation of motion and with either pain, tenderness, or both), number of joints with limitation of motion, Childhood Health Assessment Questionnaire (CHAQ), and hs-CRP (2, 3, 4). If a patient discontinues prematurely before Week 48, hs-CRP must be performed by the central laboratory at EOT.
- j* Juvenile Arthritis Disease Activity Score scoring is explained in [Section 9.4.2](#).
- k* Hematology (blood should be drawn PRIOR TO drug administration): Hemoglobin, hematocrit, red blood cell (RBC) count and morphology (if RBC count is abnormal), white blood cell (WBC) differential (neutrophils, lymphocytes, monocytes, eosinophils, basophils), platelet count, absolute neutrophil count (ANC). If a patient discontinues prematurely before Week 48, the test must be performed by the central laboratory at EOT.
- l* Chemistry (blood should be drawn BEFORE drug administration): ALT, AST, ALP, total bilirubin, conjugated bilirubin, unconjugated bilirubin, and albumin will be tested. Complete chemistry (refer to [Section 9.3.4](#)) should be done at Visit 27 EOT (Week 96 for third portion). If a patient discontinues prematurely before Week 48, the test must be performed by the central laboratory at EOT.
- m* Lipids (blood should be drawn BEFORE drug administration): Triglycerides (TG), total cholesterol, high density lipoprotein (HDL) cholesterol, low density lipoprotein (LDL) cholesterol. Patients are required to fast at least 8 hours before the test. At EOT, the test will be performed only for patient who discontinues prematurely before Week 48 and must be performed by the central laboratory.

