The entire TEAE period includes the **core treatment**, **extension treatment** (only applicable for patients who enter the extension), and **follow-up** epochs. The TEAE period in the core treatment phase includes **core-treatment** epoch for patients who enter the extension, and includes **core-treatment** and **follow-up** epochs for patients not entering the extension.

All safety analyses will be performed on the safety population, unless otherwise specified, using the following common rules:

- The baseline value is defined as the last available value prior to the first dose of the study medication.
- The potentially clinically significant abnormality (PCSA) values are defined as abnormal values considered medically important by the Sponsor according to predefined criteria/thresholds based on literature review and defined by the Sponsor for clinical laboratory tests and vital signs.
- The PCSA criteria will determine which patients had at least 1 PCSA during the TEAE period, taking into account all evaluations performed during the TEAE period, including nonscheduled or repeated evaluations. The number of all such patients will be the numerator for the on-treatment PCSA percentage.
- The treatment-emergent PCSA denominator by group for a given parameter will be based on the number of patients assessed for that given parameter in the TEAE period by dose regimen on the safety population.
- For quantitative safety parameters based on laboratory measurements, descriptive statistics will be used to summarize results and change from baseline values by visit and dose regimen. Summaries will include the endpoint value. The endpoint value is commonly defined as the value collected at the same day/time of the last dose of investigational product. If this value is missing, this endpoint value will be the closest one prior to the last dose intake.
- Analyses of the safety variables will be essentially descriptive and no systematic between-group testing is planned.

Adverse events

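### The laboratory endpoint value can never be the end-of-treatment sample, so that row is 10 or more weeks old for most completers' parameters and leaves out anything drawn after the last dose

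*SAP*

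**What the plan says.** The SAP (2.4.5, General common rules) states: "The endpoint value is commonly defined as the value collected at the same day/time of the last dose of IMP". It then gives the fallback: "If this value is missing, this endpoint value will be the closest one prior to the last dose intake". Protocol 11.4.3 opens the same way, "The endpoint value is commonly defined as the value collected at the same day/time of the last dose of investigational product", and has the same fallback. Neither document lets a later value qualify.

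The dosing calendar is in the flow-chart footnotes of Protocol 1.2.2. For a q2w regimen in the dose-finding and second portions, "then the last IMP injection will occur at Week 154"; for qw it is Week 155, and EOT is Week 156. For the third portion, "The last IMP injection will occur at Week 94", with EOT at Week 96. After premature discontinuation, "EOT will occur 1 week after the last IMP injection for Dose Regimen 3 Cohort and 2 weeks after the last IMP injection" for Regimens 1 and 2. No drug is given at the EOT visit (Visit 27).

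**The concern.** The endpoint row is the one line of the laboratory tables that lines up patients with different treatment durations at the end of their treatment. A reader will take it as the patient's state when treatment ended. If the rule cannot reach the EOT sample, the row is out of date for completers. For patients who stop early it leaves out whatever was drawn after the last dose. The parameters affected include neutrophils, platelets and ALT, each of which has its own discontinuation criterion in Protocol 10.3.3.

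**Working it through.** The plan gives no figure to reproduce. The check applies the rule to the planned calendar.

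**Inputs.**
- Last dose and EOT weeks: as above.
- Hematology and the abbreviated chemistry panel (liver tests, albumin): every extension visit up to Week 144, then EOT (Protocol 1.2.2.1). In the third portion, the last visit before EOT is Week 84 (Protocol 10.1.9.3.1).
- Full chemistry panel: screening, baseline and Week 12 (Protocol 1.2.1, footnote p), next at EOT (1.2.2.1 footnote j; 1.2.2.3 footnote l).
- hs-CRP: up to Week 144 and EOT; in the third portion, Weeks 24, 48, 72 and EOT.
- Lipids, dose-finding and second portions: last at Week 96. EOT lipids are drawn only for patients who stop before then.

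**Formulas.** Endpoint week = latest planned sample at or before the last dose. Gap = last-dose week − endpoint week. Alternative = latest planned sample through EOT.

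**Completers who stay on one regimen (weeks).**

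| Group and parameter | Last dose | Endpoint as written | Gap | Last value through EOT |
|---|---|---|---|---|
| Dose-finding/second, q2w: hematology, hs-CRP | 154 | 144 | 154 − 144 = 10 | 156 |
| Dose-finding/second, qw: hematology | 155 | 144 | 155 − 144 = 11 | 156 |
| Dose-finding/second, q2w: full-panel-only chemistry | 154 | 12 | 154 − 12 = 142 | 156 |
| Dose-finding/second, q2w: lipids | 154 | 96 | 154 − 96 = 58 | 96 (no EOT sample) |
| Third portion: hematology | 94 | 84 | 94 − 84 = 10 | 96 |
| Third portion: hs-CRP | 94 | 72 | 94 − 72 = 22 | 96 |
| Third portion: full-panel-only chemistry | 94 | 12 | 94 − 12 = 82 | 96 |

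**Patients switched to the selected regimen.** Protocol Table 1 puts the last on-treatment visit 4 to 12 weeks before EOT. On q2w that is 4 − 2 = 2 to 12 − 2 = 10 weeks before the last dose, so the 10-week gap is not universal.

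**Early stoppers.**
- Excluded because drawn after the last dose: the Day 12 blood count (Protocol 9.3.4) if no second dose follows, unscheduled samples, the EOT sample, and the confirmatory retest. Protocol 10.3.3 withholds dosing until that retest is back, so if treatment then stops for good the retest postdates the last dose.
- Example: a q2w patient stopped on the Day 12 count has had one dose. Blood on dosing days is drawn before the injection, so the endpoint is the Day 1 pre-dose value. That is also the baseline, so the change from baseline is 0.
- Kept: an abnormal pre-dose sample from the visit of the last dose whose result came back afterwards.

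**Where later values still count.** EOT is 14 or 7 days after the last dose, inside the treatment-emergent period, which runs to last dose + 60 days (SAP 2.1.4).

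**The case against.** The best defense has three parts.

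*The later values are not lost.* This stands. PCSA incidence and shift tables cover the whole treatment-emergent period. Neutropenia, thrombocytopenia and lymphopenia are graded on the lowest count in that period, and ALT is plotted at its peak. By-visit summaries admit unscheduled and local-laboratory values (SAP 2.5.5), and the visit windows in SAP Appendix B include a Week 156 row, although the hematology and chemistry columns cannot be read in the public copy. No between-group testing is planned.

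*The rule is an accepted last-value-under-dosing convention.* Protocol and SAP agree on it, and the treatment epoch ends at last dose + 13 days (q2w) or + 6 days (qw), so nominal EOT already falls in follow-up. This does not justify the exclusion. A sample 14 or 7 days after a dose sits at the same point in the dosing interval as every other scheduled pre-dose sample, and the epoch boundary misses it by one day. Nor does a convention explain a Week 12 creatinine shown as the endpoint of a treatment lasting to Week 154.

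*Values that trigger stopping are often kept.* This also stands. A reader might infer that the rule drops the very results that led to discontinuation. The documents do not support that as a general statement, because a scheduled sample drawn before the last injection and reported after it is the endpoint value. They also give no frequency for either situation, so a general bias towards normal is not shown.

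**Conclusion.** The point holds in a limited form. As written, the EOT sample can never be the laboratory endpoint. For non-switching completers the hematology endpoint is 10 weeks (q2w, third portion) or 11 weeks (qw) before the last dose, and full-panel-only chemistry goes back 142 or 82 weeks. For early stoppers, samples after the last dose are left out, and a q2w patient stopped on the Day 12 count shows no change at all. These figures assume visits and injections on their planned weeks. Lipids in dose-finding and second-portion completers would not change, because no EOT lipid sample is drawn from them.

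The harm is confined to one descriptive row. It would be wrong to infer that the safety analysis loses these data or that a safety conclusion is shown to change. It is still worth correcting, because the row does not describe the end of treatment. Two lesser faults are that both documents hedge the definition as what is common rather than stating a firm rule, and that the vital sign tables report an endpoint (SAP 2.4.5.4) while the rule is written only for laboratory measurements.

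**What to change.** Replace the definition in SAP 2.4.5 with a firm one for laboratory and vital sign summaries: the last available value up to last dose + 14 days (q2w) or + 7 days (qw), plus the visit window (3 days for q2w, 1 day for qw). State the day limits explicitly. A rule tied to the treatment epoch (+ 13 or + 6 days) would miss nominal EOT by one day. The alternative is to keep the present row and add one for the last value through EOT beside it. Either way, record it in the SAP as a change from Protocol 11.4.3.

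The cost is one SAP sentence and a small programming change; the samples are already planned. There are two small downsides. The row will include values one day or more into the follow-up epoch, which a footnote can say. An EOT assessment delayed beyond the window, which Protocol 1.2.2.1 footnote e allows at the next scheduled visit, stays excluded.

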#### **2.4.5.1 Analyses of adverse events**

##### ***Generalities***

The primary focus of AE reporting will be on TEAEs. Pretreatment and post-study AEs will be described separately.

If an AE date/time of onset (occurrence, worsening, or becoming serious) is incomplete, an imputation algorithm will be used to classify the AE as pretreatment, treatment-emergent, or post-study. The algorithm for imputing date/time of onset will be conservative and will classify an AE as treatment emergent unless there is definitive information to determine it is pretreatment or post-study. Details on classification of AEs with missing or partial onset dates are provided in [Section 2.5.3](#).

Adverse event incidence tables will present the number (n) and percentage (%) of patients in each dose regimen cohort experiencing an AE by primary SOC (sorted by internationally agreed SOC order), HLG, HLT, and PT, sorted in alphabetical order. Multiple occurrences of the same event in the same patient will be counted only once in the tables within a treatment phase. The denominator for computation of percentages is the safety population within each dose regimen cohort. In addition, the incidence and the number of events per 100 patient-years (number of events adjusted for the total duration of exposure) will be provided for AE summaries during the entire TEAE period.

Sorting within tables ensures the same presentation for the set of all AEs within the observation period (pretreatment, treatment-emergent, and post-study). For that purpose, the table of all TEAEs presented by primary SOC and PT sorted by the internationally agreed SOC order and

decreasing frequency of PTs within SOCs will define the presentation order for all other tables unless otherwise specified. Sorting will be based on results for the selected dose regimen cohort.

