1.2.2 Extension phase

In the dose-finding and second portions, only patients achieving at least a JIA ACR30 response at Week 12 will be permitted to continue to participate in the extension phase.

During the extension phase:

- Patients who were enrolled to the selected dose regimen during the core treatment phase (either during the initial dose-finding portion or directly to the selected dose regimen in the second portion) will continue on the selected dose regimen during the extension phase and will be followed-up as noted in [Section 1.2.2.1](#))
- Once the selected dose regimen has been determined, patients who were not assigned to the selected dose regimen will have their dose regimen adjusted to the selected dose regimen during the extension phase. Prior to dose adjustment, these patients will complete the assessments as noted in [Section 1.2.2.1](#). After the dose regimen is determined, the patients will have their dose regimen adjusted to the selected dose regimen at the time of their next regular scheduled visit (according to [Section 1.2.2.1](#)), which will be considered as the first visit (Visit 101 [Week 0]) as shown in the flow chart in [Section 1.2.2.2](#). These patients will then continue with the assessments as noted in [Section 1.2.2.2](#). All patients will remain on treatment until they have received up to a total of 144 weeks of sarilumab exposure calculated from Visit 12. A table to determine when the last on-treatment visit should occur and the weeks between the last on-treatment visit, and the EOT visit based on when the patient was changed to the selected dose regimen is provided in [Table 1](#). After the last on-treatment visit, patients will be scheduled for the EOT visit (Visit 27) and the EOS visit (Visit 28).
- Patients who are enrolled in the third portion with the selected dose regimen will be followed-up as noted in [Section 1.2.2.3](#).

1.2.2.1 Flow chart for patients who remain on the current dose (selected dose regimen) from the dose-finding portion or recruited directly under the selected dose regimen in the second portion

Visit	Extension phase (up to 144 weeks of sarilumab exposure from V12)														Post-treatment follow-up (6 weeks)		
	V13	V14	V15	V16	V17	V18	V19	V20	V21	V22	V23	V24	V25	V26		V27 ^a	V28 ^b

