10.4.2 General guidelines for reporting adverse events

- All AEs, regardless of seriousness or relationship to IMP/NonIMP, spanning from the signature of the ICF until the EOS as defined by the protocol for that patient, are to be recorded on the corresponding page(s) or screen(s) of the e-CRF.
- Whenever possible, diagnosis or single syndrome should be reported instead of symptoms. The Investigator should specify the date of onset, intensity, action taken with respect to IMP, corrective treatment/therapy given, additional investigations performed, outcome, and his/her opinion as to whether there is a reasonable possibility that the AE was caused by the IMP.

- The Investigator should take appropriate measures to follow all AEs until clinical recovery is complete and laboratory results have returned to normal, or until progression has been stabilized, or until death, in order to ensure the safety of the patients. This may imply that observations will continue beyond the last planned visit per protocol, and that additional investigations may be requested by the monitoring team up to as noticed by the Sponsor.
- Patients who experience an ongoing SAE or an AESI at the pre-specified study end-date, should be followed until resolution, stabilization, or death and related data will be collected.
- When treatment is prematurely discontinued, the patient's observations will continue until the EOS as defined by the protocol for that patient.
- Laboratory results and vital sign values are to be recorded as AEs only if:
 - Associated with symptoms, and/or
 - Requiring either corrective treatment or consultation, and/or
 - Leading to IMP discontinuation or modification of dosing, and/or
 - Fulfilling a seriousness criterion, and/or
 - Defined as an AESI.

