#### *Observation period*

The observation period will be divided into 5 epochs: SCREENING, TREATMENT in core period, TREATMENT in extension period, FOLLOW-UP, and POST-STUDY (defined as below):

- The SCREENING epoch is defined as the time from the signed informed consent date up to the time prior to first dose of IMP.
- The CORE TREATMENT epoch is defined as the time from first dose of IMP to last dose in core phase +13 days for patients on bi-weekly dosing or +6 days for patients on weekly dosing, or first dose of IMP in the extension period for patients who enter the extension.
- The EXTENSION TREATMENT epoch is defined as the time from first dose of IMP in extension period to last dose of IMP in extension period + 13 days for patients on bi-weekly dosing or +6 days for patients on weekly dosing. Only patients who enter the extension have the EXTENSION TREATMENT epoch.
- The FOLLOW-UP epoch is defined as the time from the end of TREATMENT epoch (ie, the end of CORE TREATMENT epoch for patients not entering in the extension period; or the end of EXTENSION TREATMENT epoch for patients who enter the extension period) to “last dose of IMP+60 days”.
- The POST-STUDY epoch is defined as the time after the “last dose of IMP+60 days”.

The entire treatment-emergent adverse event (TEAE) period includes the CORE TREATMENT, EXTENSION TREATMENT (only applicable for patients who enter the extension), and FOLLOW-UP epochs. The TEAE period for the core part includes CORE TREATMENT epoch for patients who enter the extension, and includes CORE TREATMENT and FOLLOW-UP epochs for patients not entering the extension.

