#### **2.1.4.1 Adverse events variables**

##### ***Adverse event observation period***

- Pretreatment AEs are AEs that developed or worsened or became serious during the screening epoch.
- Treatment-emergent AEs (TEAEs) are AEs that developed or worsened or became serious during the treatment and/or follow-up treatment epochs, as applicable.
- Post-study AEs are AEs that developed or worsened or became serious during the post-study epoch.

All AEs (including SAEs and AESIs) will be coded to a lower-level term (LLT), PT, high-level term (HLT), high-level group term (HLGT), and associated primary SOC using the version of MedDRA in effect at Sanofi at the time of DBL.

The occurrence of all AEs (including SAEs and AESIs) will be recorded from the time of signed informed consent until the end of the study.

Any SAE brought to the attention of the Investigator at any time after the end of the study for the patient and considered by him/her to be caused by the IMP with a reasonable possibility, should be reported to the monitoring team.

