#### **2.4.3.1 Extent of investigational medicinal product exposure**

The extent of IMP exposure will be assessed by the duration of IMP exposure, and actual dose information.

The duration of sarilumab exposure is defined as: last dose date – first dose date + 14 days (+ 7 days for dose regimen 3 cohort). These calculations are regardless of unplanned intermittent discontinuations (see [Section 2.5.3](#) for calculation in case of missing or incomplete data).

Duration of IMP exposure will be summarized descriptively as a quantitative variable (number, mean, SD, median, minimum, and maximum) and categorically by numbers and percentages of patients within each of the following categories and cumulatively according to these categories:

- 12-week core part
  - $\leq 6$  weeks
  - $>6$  and  $\leq 12$  weeks
  - $>12$  weeks
- Final study data, including extension
  - $\leq 12$  weeks (3 months)
  - $>12$  and  $\leq 24$  weeks
  - $>24$  and  $\leq 36$  weeks
  - $>36$  and  $\leq 48$  weeks

- >48 and  $\leq$  72 weeks
- >72 and  $\leq$  96 weeks
- >96 and  $\leq$  120 weeks
- >120 and  $\leq$  144 weeks
- >144 and  $\leq$  156 weeks
- >156 weeks

Additionally, the cumulative duration of treatment exposure, defined as the sum of patients' duration of treatment exposure expressed in patient years, will be provided.

The time between doses will be summarized.

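### On the visible text, adverse-event rates per 100 patient-years count events to last dose + 60 days but divide by exposure ending at last dose + 14 days (+ 7 for weekly dosing)

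*SAP*

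**What the plan says.** **Numerator.** Under Generalities, SAP 2.4.5.1 states that "the incidence and the number of events per 100 patient-years (number of events adjusted for the total duration of exposure) will be provided" for summaries over the whole treatment-emergent period. SAP 2.1.4 defines that period: "The entire treatment-emergent adverse event (TEAE) period includes the CORE TREATMENT, EXTENSION TREATMENT (only applicable for patients who enter the extension), and FOLLOW-UP epochs". The follow-up epoch closes 60 days after the last dose. SAP 2.1.4.1 accordingly treats as treatment-emergent all "AEs that developed or worsened or became serious during the treatment and/or follow-up treatment epochs, as applicable". Protocol 11.4.3 gives the reason for the 60 days: to capture events within about five half-lives of the last dose.

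**Divisor.** SAP 2.4.5.1 names the total duration of exposure and gives no cross-reference. SAP 2.4.3.1 reads "The duration of sarilumab exposure is defined as: last dose date", minus the first dose date, plus 14 days, or plus 7 days for Dose Regimen 3. The same section sums these durations, and that cumulative "duration of treatment exposure expressed in patient years, will be provided". Protocol 11.4.1.1 has the same definition.

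**Routine collection.** Protocol 10.4.2 has adverse events recorded over a period "spanning from the signature of the ICF until the EOS as defined by the protocol for that patient". After premature stopping, protocol 1.2.2.1 says "EOT will occur 1 week after the last IMP injection for Dose Regimen 3 Cohort and 2 weeks after the last IMP injection" for the two q2w regimens. The end-of-study visit comes 6 weeks after that.

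**Early stopping by design.** For those enrolled before the third portion, protocol 1.2.2 sets a response gate: "only patients achieving at least a JIA ACR30 response at Week 12 will be permitted to continue to participate in the extension phase". The third portion has no such gate.

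**The concern.** A rate per patient-year should draw its events and its person-time from the same window. Here the event window appears to be longer than the person-time window by a fixed number of days for every patient who has stopped. Events in that tail raise the numerator and add nothing to the divisor, so the rate is overstated.

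Because the unmatched time is fixed per stopped patient, its relative weight is small after three years of dosing and larger after twelve weeks. The size of the bias therefore depends on how many patients stop early, and the ACR30 gate makes some early stopping part of the design. Long-term safety is a secondary objective, and SAP 2.1.4 makes safety a primary objective of the extension, so these rates will be read. Nothing confirmatory depends on them: the safety analyses are descriptive, with no systematic between-group testing.

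**Working it through.** The documents state no figure for this gap or for an event rate, so there is nothing to reproduce. The exposure formula can be checked against the schedule. A last dose at Week 154 (q2w) gives 154 × 7 + 14 = 1092 days, and Week 155 (weekly) gives 155 × 7 + 7 = 1092 days. Both equal 156 weeks, the planned 12 + 144.

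**Step 1: days without person-time per stopped patient**

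- SAP window: 60 − 14 = 46 days (q2w); 60 − 7 = 53 days (weekly).
- Routine collection to end of study: (14 + 42) − 14 = 42 days (q2w); (7 + 42) − 7 = 42 days (weekly).

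The 42-day figure is the more realistic, because after end of study the protocol asks only for serious or special-interest events that the investigator attributes to the product.

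**Step 2: exposure per patient on a q2w selected regimen**

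- Dose-finding and second portions, completer: 1092 days.
- Third portion, last dose Week 94: 94 × 7 + 14 = 672 days.
- Gate failure with last dose at Week 12: 84 + 14 = 98 days. Protocol 1.2.1, footnote j, releases the ACR30 result only after Visit 12.

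**Step 3: pooled overstatement at the final analysis**

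Planned patients on the selected regimen: 12 (dose-finding, 6 per weight group) + 24 (second portion) + 28 (third portion) = 64. Let *f* be the fraction of the first 36 who stop at Week 12, with everyone else completing. The documents give no value, so *f* is an assumption.

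Exposure days = 36*f* × 98 + 36(1 − *f*) × 1092 + 28 × 672.

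Unmatched days = 64 × 42 = 2688, or 64 × 46 = 2944 on the SAP window.

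Overstatement of the number of events per patient-year = unmatched days ÷ exposure days, if the event rate off treatment equals the rate on treatment. It is half that if the off-treatment rate is half.

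| *f* | Exposure days | 42 days, equal rate | 46 days, equal rate | 42 days, half rate | 46 days, half rate |
|---|---|---|---|---|---|
| 0 | 58,128 | 4.6% | 5.1% | 2.3% | 2.5% |
| 0.25 | 49,182 | 5.5% | 6.0% | 2.7% | 3.0% |
| 0.50 | 40,236 | 6.7% | 7.3% | 3.3% | 3.7% |

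**Step 4: sensitivity to two soft inputs**

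- *Last dose of gate failures.* Protocol 10.1.7 gives the Visit 12 dose to patients going on to the extension. If gate failures last dosed at Week 10, their exposure is 70 + 14 = 84 days. At *f* = 0.5 the total is 18 × 84 + 18 × 1092 + 18,816 = 39,984, and 2688 ÷ 39,984 = 6.7%, unchanged to one decimal.
- *Evaluable versus treated.* The 12 + 24 are evaluable counts, while the safety population is all treated patients. The synopsis plans about 72 enrolled for about 60 evaluable. Scaling 36 by 72/60 gives 43.2, or 71.2 patients in all and 71.2 × 42 = 2990.4 unmatched days. At *f* = 0 this is 2990.4 ÷ (43.2 × 1092 + 18,816) = 4.5%. At *f* = 0.5 it is 2990.4 ÷ (21.6 × 98 + 21.6 × 1092 + 18,816) = 6.7%.

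Neither input moves the range materially.

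**The case against.** The strongest objection is that the decisive text may exist but not be public. Protocol 11.4.3 leaves exposure-adjusted safety methods to the SAP. The SAP contents list 2.4.5.6, on additional methods for safety variables, and 2.4.11, on analyses after dose adjustment. Neither is in the public copy, and either could define person-time. SAP 2.4.5.1 does not cite 2.4.3.1, and the two sections word the quantity differently. This stands: the mismatch is a reading of the visible text, and the request must be conditional. What remains is that 2.4.5.1 names its own divisor without citing 2.4.5.6, and 2.4.3.1 holds the only definition a reader can find.

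It can also be said that the 60-day tail is deliberate, that the error is conservative, and that summaries for 0–12, 0–24 and 0–52 weeks are planned alongside. All true, and they keep the priority low. They do not justify an unstated mismatch within a single rate.

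Three stronger readings are tempting and are not supported:

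- A reader might take 46 or 53 days as the lost time. That is the nominal window; routine collection ends at the end-of-study visit, which leaves about 42 days.
- A reader might note that for one patient last dosed at Week 12 the excess is 42 ÷ 98 = 43%, or 53 ÷ 91 = 58% on weekly dosing with the full window, and infer a bias of that order. The SAP reports pooled rates, in which such patients contribute little exposure.
- A reader might infer that events in the non-selected regimens are cut at dose adjustment while exposure is not. SAP 2.4.5 already restricts summaries of those regimens to data before the first adjustment, which can naturally be read to include exposure. Patients who switch carry no 60-day tail there.

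**Conclusion.** The point holds as a conditional, minor one. On the visible text, event rates over the entire treatment-emergent period use a longer window for events than for person-time. For a q2w selected regimen at the final analysis, the pooled overstatement is roughly 2% to 7%. The low end has no early stopping and half the event rate off treatment. The high end has half of the 36 gated patients stopping at Week 12, an equal event rate off treatment and the full SAP window.

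This assumes that the divisor is the 2.4.3.1 quantity, that all patients have stopped treatment and that those outside the gate complete. It applies to numbers of events, not to patients counted once. At an interim cut-off, patients still on treatment carry no tail, so the effect is smaller. The bias grows with early stopping, so it could differ between small regimen cohorts, but the documents give no stopping figures from which to size such a difference. Crude percentages are unaffected, and no test or sample size depends on the rate.

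**What to change.** First check whether SAP 2.4.5.6 or 2.4.11 already defines person-time for these rates. If so, a cross-reference in 2.4.5.1 is enough. If not, add one of the following to 2.4.5.1:

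- Define patient-years for treatment-emergent event rates as time from first dose to the earliest of last dose + 60 days, end of study or last contact, data cut-off, or, for non-selected regimens, the first adjusted dose.
- Or keep exposure as defined in 2.4.3.1 as the divisor and limit the numerator of the rate to events in the core and extension treatment epochs.

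In either case keep every treatment-emergent event in the incidence tables, including serious events that start between end of study and day 60, and footnote any that fall outside the rate window.

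The cost is one or two sentences in the SAP and, for the first option, one derived time-at-risk variable. No new data are needed.
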